With the continuous development and clinical popularization of invasive blood pressure monitoring technology (ABP), the safety of patient anesthesia has been greatly guaranteed. The radial artery is superficial, and the forearm has a dual blood supply to the radial and ulnar arteries, thus becoming an arterial puncture

The first choice for catheterization.

It has been reported that the distal quarter of the forearm is the best insertion site for ultrasound-guided radial artery puncture, and the selection of the radial forearm catheterization improves the success rate and the overall success rate of the first puncture attempt

Prevalence of hematoma during the puncture process.

Invasive radial artery puncture sometimes cannot completely avoid complications, such as puncture hematoma and artery closure. Complications such as plug, infection, pseudoaneurysm, vasospasm, and neurovascular injury have been reported in the literature.

There are no recommendations for the best puncture site for radial artery puncture. Therefore, the choice is more appropriate and safe. Fully accurate location as ultrasound-guided radial artery puncture and catheterization is particularly important.

2. purpose of research

1. Main objective: To evaluate the anatomical parameters of the radial artery based on ultrasound imaging in the forearm,

Provide a reference to ultrasound anatomy for the clinical implementation of radial artery puncture.

2. Secondary objective: To find the best site of radial artery puncture to improve the safety and accuracy of radial artery puncture and catheterization.

3. Study design, methods, and study procedures

1. Study design

In this study, we plan to further compare the position distance between the radial artery and the ulnar artery, the vertical distance from the radial artery (center), and the distance between the radial artery (ulnar: radial)

The influence of age, BMI and left and right side on the radial artery position.

At the same time, the radial movement is intended to be guided by ultrasound at different distances during the radial artery puncture

Success rate of first puncture, puncture catheterization time, number of puncture and puncture related complications.

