The sample size of this study was calculated according to the results of the pretest. The main observation indicators were the vertical distance between the radial artery and the radial artery (radial artery), set statistical efficiency $1 - \beta = 0.9$, test standard $\alpha = 0.05$, $n = 30$, calculated $n = 30$, the case loss rate was set at 15%, and the final sample size was 100 example.

2. Research methods

The anatomical relationship and influencing factors of the radial artery were observed by ultrasound, and then the optimal puncture position was selected and the puncture was guided Reduce the number of punctures, reduce the complications, and improve the safety and precision.

3. Study steps

Main study steps: patients in the supine position, both upper limb abduction, palm up, wrist angle of 45°, using a portable ultrasound instrument (probe frequency 13–6 MHz, Sonosa), the ultrasound probe in the direction of the short axis in the radial artery (from the radial artery) to the radius for the projection of the radial artery, the relative distance of each anatomical site was 2cm. There was no significant compression of the radial artery to maintain the normal shape and site of the vessel. The radial diameter of the radial artery, the vertical distance from the skin, and the radial god were measured Distance relative to the radial artery (ulnar: radial). And recorded according to gender, age, BMI, and left and right sides.

Secondary study objective steps: the radial artery surface projection was divided into three sections. The first segment is in the

range of 0–5cm from the proximal to the radial stem, the second segment is in the range of 5–10cm from the proximal to the radial stem, and the third segment is in the range of 10cm to the proximal cubital fossa. And the puncture site was divided into the first stage of the left hand, the second section of the left hand, the third section of the left hand, the first section of the right hand, the second stage of the right hand, and the third section of the right hand; the experimenter randomly selected the puncture site, and used the portable ultrasound instrument (probe frequency 13–6 MHz, Sonos), and the in-plane puncture technique was used to puncture the radial artery, and the first puncture success rate, puncture insertion time and puncture times were recorded

And puncture-related complications.

4. Case selection

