1. Inclusion criteria: (1) patients undergoing elective surgery scheduled to undergo general anesthesia and invasive arterial blood pressure monitoring; (2) ASA grade I~; (3) age 18 to 65 years; (4) agree to participate in this clinical study and sign the informed consent form.

2. Exclusion criteria: (1) Allen positive or suspicious positive patients; (2) peripheral vascular diseases; (3) coronary artery related diseases; (4) local skin infection, rupture, scar and surgical history; (5) shock patients or acceptance, heart drugs, vasoreduction drugs; (6) peripheral nerve injury, anatomical abnormalities and neurological abnormalities; (7) upper limbs

The atic, not unable to complete the ultrasound assessment.

3. Termination criteria: Patients may withdraw their consent and withdraw from the trial at any time.

Any medical condition in the study that poses a risk that the continuing study subject may be terminated by the study physician

Continued to participate in this study;

And the study physician may terminate if the patient fails to comply with the study plan, or if a study-related injury occurs

Continue to participate in this study;

The investigator judged the other conditions that should be withdrawn from the trial.

5. Other alternative methods of diagnosis and treatment are available

If the radial artery puncture is unsuccessful, non-invasive blood pressure monitoring of the upper arm cuff is feasible.

Vi. Test items and test time points

After entering the patient into the room, the position distance between the radial artery (the radial artery, radial artery, radial artery, radial artery (center) vertical distance from the skin, and the distance of the radial nerve (ulnar: radial side) were measured. At the same time, the first puncture of radial artery puncture at different distances of the forearm was recorded

Power, puncture and catheterization time, number of puncture times, and puncture-related complications.

7. Efficacy evaluation criteria

Complete and accurately record all data, operation time, frequency and success rate.

Viii. Observation, recording and disposal of adverse events

You will be followed up and evaluated within 3 days of the study. In case of serious radial artery puncture complications during the experiment, the experiment will be stopped immediately, and the adverse events will be recorded and reported to the project leader. Positive and effective

Follow-up records according to the type of complications.

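### The enrolment figure of 100 does not follow from the printed calculation (n = 30, 15% loss), and the SAP does not say what 30 counts

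*SAP*

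**What the plan says.** The sample-size paragraph in section 3 of the SAP (under 1. Study design) bases the calculation on a pretest, with a vertical distance of the radial artery as the main indicator. Its design settings are "set statistical efficiency $1 - \beta = 0.9$, test standard $\alpha = 0.05". It then ends: "calculated $n = 30$, the case loss rate was set at 15%, and the final sample size was 100 example".

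The scenario summary also gives 100 as the total number of cases, so 100 is not a single misread digit.

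The pretest difference and standard deviation are not given. Neither is the unit of 30 or the number of groups. The figure is also printed twice in a row ("n = 30$, calculated $n = 30$, the case loss rate was set at 15"), the first time where an input would normally stand.

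Two other parts of section 3 bear on how 30 might be read:

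- The main study steps describe measurement with "patients in the supine position, both upper limb abduction, palm up", and continue: "And recorded according to gender, age, BMI, and left and right sides".
- The steps for the secondary objective divide the artery into three segments, and therefore six hand-by-segment puncture sites. The sample-size paragraph mentions neither number.

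**The concern.** The paragraph reads as one derivation: settings, calculated n, loss allowance, final number. A reader who applies 15% loss to 30 expects about 36 and finds 100. The 100 is the enrolment that the study relies on, so it should either be reproducible or be described as chosen on other grounds.

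The missing unit matters because the possible readings point in opposite directions. On one, the trial enrols far more patients than the calculation asks for. On another, it falls slightly short of its own requirement. The printed text does not let a reader tell which applies.

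**Working it through.** **Inputs.** Calculated n = 30, loss 15% and final n = 100, all from the sample-size paragraph; 100 also from the scenario summary. The step from power 0.9 and alpha 0.05 to n = 30 cannot be recomputed, because no effect size or standard deviation is given. Only the step from 30 to 100 can be tested.

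**Formulas.** For k groups of 30:

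- standard allowance: 30k / (1 − 0.15)
- common shortcut: 30k × 1.15

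Each was rounded up once on the total and once per group. Per group, 30/0.85 = 35.3 → 36 and 30 × 1.15 = 34.5 → 35.

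| k | 30k | 30k/0.85, rounded on total | 36k | 30k × 1.15, rounded on total | 35k | Range |
|---|---|---|---|---|---|---|
| 1 | 30 | 36 | 36 | 35 | 35 | 35-36 |
| 2 | 60 | 71 | 72 | 69 | 70 | 69-72 |
| 3 | 90 | 106 | 108 | 104 | 105 | 104-108 |
| 4 | 120 | 142 | 144 | 138 | 140 | 138-144 |
| 5 | 150 | 177 | 180 | 173 | 175 | 173-180 |
| 6 | 180 | 212 | 216 | 207 | 210 | 207-216 |

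**Reproducing the plan's figure.** It is not reproduced. The result rises with k and jumps from at most 72 (k = 2) to at least 104 (k = 3), so no whole-number k gives 100. Three groups without any loss allowance give 90, which also misses.

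**Working backwards.** 100 × 0.85 = 85 evaluable patients, and 85/30 = 2.83 groups. With the shortcut, 100/1.15 = 87.0, and 87.0/30 = 2.90 groups. Neither is a whole number.

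**Size under the readings of 30.**

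- *30 is the total number of patients:* 36 are needed, and 100/36 = 2.8 times the requirement.
- *30 per segment, three segments (assumption):* 85/3 = 28.3 per segment, against 30. Enrolment is 4 to 8 below the 104-108 needed.
- *30 per puncture site, six sites (assumption):* 85/6 = 14.2 per site, against 30. Nothing in the text connects the six sites to the calculation.

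**Illustrative power only.**

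- Suppose 30 is patients in a paired comparison at two-sided 0.05. Then 90% power at n = 30 corresponds to a standardized paired difference of 0.612. At 85 patients the same difference has power above 99.9%, and the difference detectable with 90% power is 0.356, or 0.58 times as large.
- Suppose instead a three-group ANOVA sized for 90% at 90 patients. Power at 85 is about 88%.

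The SAP states neither design for the calculation. The mismatch does not depend on either.

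**The case against.** The strongest defence is that the sentence is visibly damaged. The description of the main indicator is garbled and n = 30 appears twice, so a term was probably lost in translation or text extraction. That term may have been the unit or the group count, and the original may state what seems to be missing. This stands in part: one should not be certain that the sponsor never stated the unit. It does not rescue the arithmetic. A lost effect size or standard deviation would explain how 30 arose, but not how 30 and 15% become 100. A lost group count does not help either, since no whole number of groups gives 100.

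A second defence is that the intention was three segments of 30, rounded to 100. The text does not say so. The segments belong to the secondary puncture steps, whereas the calculation concerns vertical distance. On that reading the SAP's own allowance needs at least 104, although the shortfall is small.

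A third defence is that enrolling more than the minimum does no harm. This stands if 30 is the total: no power is lost, and the fault is an unexplained figure.

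A reader might go further and infer that the 90% is wrong because the enrolled study would have a different power. The document does not support that. The 0.9 is a setting of the calculation, and the SAP does not claim 90% at 100 patients. A reader might also take the near-100% paired power as the study's actual power. That needs 30 to be patients in a paired comparison, while the statistical section names ANOVA between groups and a t test.

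**Conclusion.** The point holds as a mismatch between printed numbers. The SAP presents 100 as following from n = 30 and 15% loss, and it does not follow under either usual loss formula, either rounding convention or any whole number of groups. Confidence in this is high, and it rests on no assumption about the effect size or the test.

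The consequence is less certain. If 30 is the total, 100 is about 2.8 times the requirement with no loss of power. If 30 is per segment, the study is slightly short, at 28.3 evaluable per segment. The printed text does not settle which reading applies, so neither a loss nor a surplus of power can be claimed as fact. The point should be fixed, but it does not threaten the feasibility of the study.

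**What to change.** Keep 100 patients and revise the sample-size paragraph as follows:

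1. State what 30 counts (total patients, or patients per group, segment or site) and the number of groups in the calculation.
2. Either correct the step from 30 and 15% loss to 100, or state that 100 was chosen independently of the calculated requirement.
3. Keep 90% as the design input for the calculated n. Using the pretest difference and standard deviation that the sponsor holds, add the power for vertical distance at the 85 patients expected to be evaluable.

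The cost is wording and one short calculation from pretest data. No extra patients are needed. The added power figure may differ from 90%.

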The research plan

Clinical study protocol for safety and precision of radial artery catheterization

Research unit: Nanjing First Hospital

Department undertaken by: Department of
Anesthesiology

Contact number: [name]

Participating units: Nanjing Jiangning Hospital of
Traditional Chinese Medicine

Years of study: July 2023–June 2024

Version number: V1.0

Version date: 22nd July, 2023

scenario summary

research design (Can be selected more)	 case-control study  cohort study  cross-sectional study  Randomized controlled study  applied the blind method  other:
Study type (Please follow the project)	 Concomitant diagnostic kit study  Retrospective study of previous clinical data
Type check	 Retrospective study of previous clinical specimens  Establish a specimen library study  Establish a cohort study  Previous individual cases were reported  Study of non-implantable medical devices (face mask, dental pad, etc.)  Five years of marketed drug study (including chemical drugs, generic drugs, etc.)  Listed device study (including AI, imaging software)  Others (for the investigator's judgment, please specify:)
Total number of cases	100 Cases
Risk / benefit analysis	
Risk: The study may have a radial artery puncture injury;
 
Benefits: Select a more appropriate and safe and accurate location for clinical practice as an ultrasound-guided radial artery puncture placement
 
Pipe parts.

risk judgement	 Not greater than the minimum risk  is greater than the minimum risk
	Minimum risk: the likelihood and extent of expected risk in the trial is not greater than routine or routine

	Risk of grid examination or psychological testing
The study period	From 22 July 2023 to 30 June 2024

1. research background

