IX. Research quality control and quality assurance

not have

X. Data security monitoring

The clinical study will develop a corresponding data safety monitoring plan according to the risk size. All bad events should be recorded in detail, properly handled and tracked until properly resolved or in stable condition, and timely submitted to the ethics committee and the competent department in accordance with the regulations. Door, sponsor and drug to report serious adverse events and unexpected events; principal investigator regularly

A cumulative review of all adverse events and an investigator meeting if necessary to assess the risks and benefits of the study; both Emergency unblinding may be performed when necessary to ensure subject safety and equity.

Xi. Statistical treatment

Using SPSS 22.0 software, the measurement data with mean \pm standard deviation ($\bar{x} \pm s$), ANOVA between groups; count data are presented as example or percentage, with t test, $P < 0.05$. The difference was statistically significant.

Xii. Ethics principles and requirements for clinical research

Clinical studies will follow the Declaration of Helsinki of the World Medical Congress and the Measures of the National Health and Family Planning Commission of the People's Republic of China, and implement informed consent,

Protect privacy, research free and compensation, risk control, special subject protection and compensation principles and requirements for research related damages. The clinical study was performed before EC approval of the study protocol. Before each subject is enrolled in the study, the Investigator has the responsibility to fully and comprehensively present the purpose, procedures and possible risks of the study, and their legal representative and to sign a written informed consent form that their participation in the clinical study is entirely voluntary, that they may refuse to participate or withdraw from the study at any stage of the trial without discrimination and retaliation, and their medical treatment and interests are not affected. The informed consent form should be kept as a clinical study document for future reference to effectively protect the personal privacy and data confidentiality.

Xiii. Research progress

July 2023–August 2023: Trial implementation

August 2023–March 2024: Collect and collate data

March 2024– June 2024: Writing the paper

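### The puncture-site comparison leaves site selection to the experimenter and makes no provision for operator or hospital, so a skill difference could be read as a site effect

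*SAP*

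**What the plan says.** The scenario summary ticks "Randomized controlled study" and leaves the blinding box unticked. The title page gives "Research unit: Nanjing First Hospital" and, under "Participating units: Nanjing Jiangning Hospital of", a second hospital. What that second hospital does (enrolment, scanning, puncture or data work) is not stated.

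In the study steps for the secondary objective, the artery is split into three segments on each arm, which makes six sites: "the puncture site was divided into the first stage of the left hand, the second section of the left hand", and so on. Then "the experimenter randomly selected the puncture site". No list, ratio, blocking or concealment follows. The same sentence continues: "the in-plane puncture technique was used to puncture the radial artery, and the first puncture success rate, puncture insertion time and puncture times were recorded", with puncture-related complications added. The ultrasound measurements are "recorded according to gender, age, BMI, and left and right sides". The test-items section lists the same puncture outcomes again. Operator, hospital and the order of punctures appear in none of these places.

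The statistical treatment section names ANOVA and a t test, with no term for operator or hospital. Under "IX. Research quality control and quality assurance" the whole entry is a two-word negative.

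**The concern.** Success at first puncture, time to catheterisation, number of attempts and complications all depend on the hands doing the work. The secondary objective is to name the best site, so the segment comparison has to be free of any link between who punctures and where.

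The plan leaves the site to the experimenter's own selection and describes no device that would keep it random. Suppose a more practised operator tends to take one segment, or one segment is tried more often once experience has grown. The segments then differ in skill as well as in anatomy. With no operator code or running puncture number provided for, the planned data would neither show such a link nor allow adjustment for it. The recommendation on site could then partly reflect the operator.

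**Working it through.** **Inputs from the SAP.** Total 100 patients, three segments on each of two arms. The stated total is used here only as a divisor. (It does not follow from the stated n = 30 and 15% loss for one, two, three or six groups, which give 36, 71, 106 and 212 by n/(1 − 0.15). That is a separate matter and does not affect this point.) With one puncture per patient and equal allocation, both assumed, there are 100/3 ≈ 33 patients per segment and 100/6 ≈ 17 per site.

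**Assumed inputs.** The SAP gives no success rates, no operator numbers and no shares of work. Take two operators with first-attempt success of 90% and 65%, a gap of 25 points, with other gaps shown below.

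**Step 1: bias if operator and site are linked.** False difference between two segments = (difference in the better operator's share) × (gap in success).
- Share differs by 30 points: 0.30 × 25 = 7.5 points.
- Shares differ completely: 1.00 × 25 = 25 points.

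**Step 2: how often this yields a false finding.** Simulated three-group chi-square test at 0.05, 34 patients per segment, no true site effect. The shares are the better operator's in segments 1/2/3. Each cell gives the false first-versus-third difference, then the false-positive rate.

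| Success rates | 50/50/50 | 70/50/30 | 80/50/20 |
|---|---|---|---|
| 90% v 80% | 0; 5% | 4 points; 7% | 6 points; 9% |
| 90% v 70% | 0; 5% | 8 points; 10% | 12 points; 19% |
| 90% v 65% | 0; 5% | 10 points; 13% | 15 points; 25% |
| 90% v 60% | 0; 5% | 12 points; 16% | 18 points; 32% |

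With operators spread evenly, the error rate stays at its nominal level whatever the skill gap.

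**Step 3: what remains under genuine random allocation.** With equal shares, mean success is (0.90 + 0.65)/2 = 0.775.
- Total variance per patient: 0.775 × 0.225 = 0.1744.
- Part due to operator: 0.5 × 0.5 × 0.25² = 0.0156, and 0.0156/0.1744 ≈ 9%.
- Standard error of a difference between two segments of 33: √(2 × 0.1744/33) = 10.3 points, a 95% range of about ±20 points.
- Chance imbalance in operator share: SD √(2 × 0.25/33) = 0.123. Times 25 this is 3.1 points, and times 1.96 it is ±6.0 points.

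The ±6 points lies inside the ±20 and is not added to it. Removing the operator part by stratification would lower the standard error to √(2 × (0.1744 − 0.0156)/33) = 9.8 points.

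**The case against.** The strongest reply is that the plan calls itself randomised and says the site is selected at random. If that is so, operator skill cannot bias the comparison, and the ordinary test already allows for chance imbalance. This stands. A reader might infer that the site comparison is uninterpretable even with a proper random sequence because the groups are small. Step 3 shows that it is not: the ±6 points is part of the error that the 5% level already covers.

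A reader might also infer that punctures are done at both hospitals by several operators. The SAP states neither. It gives no role for the second hospital and speaks of the experimenter in the singular. With one operator, between-operator confounding disappears, although growing experience and a preference for certain sites could still be linked to segment.

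It is also fair to say that the negative entry on quality control may be a translated template field and does not address operator allocation, and that operator codes may sit on a case form or in another document not shown. So the supportable statement is that this document does not provide for them, not that they will go unrecorded. Against that, the document titles itself a clinical study protocol, has its own quality-control section, and lists its recorded items twice without the operator.

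Finally, the matter touches only the secondary objective. The main objective and the sample size rest on ultrasound anatomy, which puncture skill does not affect.

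**Conclusion.** The point holds in a limited form and is best treated as a cheap improvement. The weakness is the combination of experimenter selection without a described procedure and no provision to record, balance or model operator or hospital. Bias arises only if that selection links operator or experience to site, and the SAP does not show that it does. If it does, the false difference is 7.5 points for a 30-point difference in share at assumed rates of 90% and 65%. Across the linked scenarios tabulated it runs from 4 to 18 points, with false-positive rates of 7% to 32%. All of these rest on two operators and assumed success rates and shares. If selection is truly random, the gain from stratifying is precision alone, about 9% of the variance on the same assumptions.

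**What to change.** Replace selection by the experimenter with an allocation list of puncture segments prepared in advance, blocked within operator so that each operator punctures every segment about equally often. In place of the negative quality-control entry, require operator code, hospital and that operator's running puncture number on every case form. Stratify the segment comparison by operator.

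If there are many operators, block and stratify by hospital instead: ten operators would have about 10 patients each, fewer than two full blocks over six sites. If there is a single operator, say so in one sentence and keep the list and the running number, so that a learning effect can still be examined.

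The cost is three case-form fields and one list per operator or hospital, with no extra patients or procedures. The downsides are that operators must keep to the list and that stratifying uses a few degrees of freedom. The change belongs before data collection, because operator identity is hard to recover reliably afterwards.

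### Between-groups ANOVA is the only method named for ultrasound readings taken repeatedly along the same artery; applied as written to site, or to side at a given site, it ignores the within-patient pairing

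*SAP*

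**What the plan says.** The SAP describes the scan under Study steps (main study steps). The patient is positioned as "patients in the supine position, both upper limb abduction, palm up", the probe is moved along the radial artery, and "the relative distance of each anatomical site was 2cm". Of the readings it says "The radial diameter of the radial artery, the vertical distance from the skin, and the radial god were measured"; section Vi makes clear that the third is the distance to the radial nerve. Section Vi places the readings in one session: "After entering the patient into the room, the position distance between the radial artery". They are "And recorded according to gender, age, BMI, and left and right sides", and the Study design section lists as a question "The influence of age, BMI and left and right side on the radial artery position".

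For the analysis, section Xi offers one line for continuous data: "the measurement data with mean \pm standard deviation ($\bar{x} \pm s$), ANOVA between groups". It does not say which groups are meant. Nowhere does the document name a paired test, repeated-measures ANOVA, a mixed model or a patient effect.

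The planned size is given as "the case loss rate was set at 15%, and the final sample size was 100 example".

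**The concern.** Several readings along one artery belong to one patient, so site is a within-patient factor. If both arms are scanned, side at a given site is one too. Between-groups ANOVA treats the readings as if each came from a different patient. The variation between patients cancels in a within-patient difference, but this method leaves it in the error term.

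The study wants to describe where the artery lies and to look for a good puncture site. If differences between sites or sides are tested in this way, their confidence intervals are wider than the data warrant and moderate real differences can be missed. This goes beyond missing detail, because section Xi states a method and that method does not suit the readings that serve the main objective.

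**Working it through.** **Inputs.** From the SAP: 100 patients, 15% loss (100 × 0.85 = 85 left), α = 0.05, power 0.90. Not in the SAP, and so assumed: within-patient correlation r = 0.3, 0.5 or 0.7; a two-sided test; five or six sites where a number is needed. The SAP gives no standard error, correlation or detectable difference for these comparisons, so there is no figure of its own to reproduce. Normal quantiles are 1.96 and 1.2816 (sum 3.2415 before rounding).

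**1. Two sites, or left versus right at one site, equal SDs.** The between-groups standard error is √(2/n) in SD units; the correct paired one is √(2(1−r)/n). Their ratio is 1/√(1−r).

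| | r = 0.3 | r = 0.5 | r = 0.7 |
|---|---|---|---|
| SE ratio, 1/√(1−r) | 1.20 | 1.41 | 1.83 |
| True null rejected, 2[1−Φ(1.96/√(1−r))] | 1.9% | 0.6% | 0.03% |
| Power where a paired test has 90%, Φ(3.2415 − 1.96/√(1−r)) | 82% | 68% | 37% |

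The sample size cancels from all three rows. Simulation at n = 100 agrees (power 81%, 67%, 37%).

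**2. Smallest difference detectable with 90% power, in SDs of one reading.** Paired: 3.2415·√(2(1−r)/n). Between-groups: √(2/n)·(1.96 + 1.2816·√(1−r)).

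| | r = 0.3 | r = 0.5 | r = 0.7 |
|---|---|---|---|
| n = 100, paired | 0.38 | 0.32 | 0.25 |
| n = 100, between-groups | 0.43 | 0.41 | 0.38 |
| n = 85, paired | 0.42 | 0.35 | 0.27 |
| n = 85, between-groups | 0.47 | 0.44 | 0.41 |

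**3. Neighbouring sites more alike.** Take six sites, a patient share of 0.3 of the variance, and AR(1) correlation 0.5 in the rest. Adjacent sites: r = 0.3 + 0.7 × 0.5 = 0.65, ratio 1/√0.35 = 1.69. First versus last: r = 0.3 + 0.7 × 0.5⁵ = 0.322, ratio 1.21. In simulation the overall site test rejects a true null in about 0.3% to 0.4% of runs.

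**4. Unequal SDs.** Take six sites with SDs 1, 1, 1, 1, 1.5, 1.5 and r = 0.3. The pooled variance is (4 × 1 + 2 × 2.25)/6 = 1.417. For the two most variable sites, between-groups over true standard error = √(2 × 1.417)/√(2 × 2.25 × 0.7) = 0.95, and the type I error is about 6.3%. At r = 0.5 the ratio is √(2.833/2.25) = 1.12 and the reversal is gone.

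**5. Side tested on rows pooled over m sites.** With variance shares p (patient), a (arm) and e = 1 − p − a, true over naive standard error = √(m(a + e/m)) = √(ma + e).
- p = 0.4, a = 0.2, e = 0.4: 1.18 at m = 5 and 1.26 at m = 6; type I error 9.8% and 12.1%.
- p = 0.4, a = 0, e = 0.6: 0.775; type I error 1.1%.
- Break-even at a = p/(m − 1), which is 0.08 at six sites when p = 0.4.

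So in this layout the direction depends on how much of the variation is specific to the arm.

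**The case against.** The strongest objection is that the SAP never says the 2-cm sites are to be tested against each other. The main objective is descriptive, and the factors named for artery position are age, BMI and side. The document does define groups elsewhere, the six arm-by-segment puncture sites, and between-groups ANOVA of a once-per-patient outcome suits those. The English is also visibly a rough translation, so the phrase may mean only that groups are compared by ANOVA. This stands in part, and is why the point is conditional. It does not remove the point: the Study design section speaks of comparing these distances, side is a stated question, and section Xi names no other method for the readings. If repeated-measures ANOVA was meant, the text should say so.

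Scanning of both arms is likewise inferred from the posture and from the recording of side. The site argument needs only one arm; the side argument needs both.

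Three stronger readings are tempting and are not supported:
- *That the plan definitely compares sites with the wrong test.* The groups are undefined.
- *That the error is always conservative.* Steps 4 and 5 show exceptions.
- *That the tests of age, BMI and sex are badly anti-conservative.* If all rows from two arms and five sites were pooled as independent, a two-group comparison between patients would have a type I error of about 40% under the shares p = 0.4, a = 0.2. But no section says rows are pooled, and one value per patient at each site and arm would be valid. This is a request for clarification.

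It is also fair to say that conservative tests cost efficiency rather than credibility, and that the loss can be repaired at analysis.

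**Conclusion.** The concern holds in conditional form and should be fixed before analysis. Applied as written to site, or to side at a given site, the stated method discards the pairing. The power loss is modest at a correlation of 0.3 (90% to 82%) and serious at 0.7 (90% to 37%). These sizes rest on assumed correlations and on similar SDs across sites; the SAP gives neither. Under unequal SDs a single contrast may be slightly anti-conservative, and for side on pooled rows the type I error ran from about 1% to 12% under the assumed variance shares. The mean and SD at each site, which serve the main objective, are not affected, and large differences would be found either way. Confidence is medium, because the ANOVA groups and the arms scanned have to be inferred.

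**What to change.** In section Xi, specify a within-patient analysis for the ultrasound readings, by either route:

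- **Repeated-measures ANOVA for site with a Greenhouse-Geisser correction**, paired (not pooled-error) contrasts between sites, and a paired left-right comparison at each site with a stated multiplicity adjustment. The correction matters. Under step 3, uncorrected repeated-measures ANOVA rejected a true null in about 7% of runs, against 4.8% with the correction, and its pooled-error standard error for first versus last site is 0.87 of the true one.
- **One linear mixed model**, with random effects for patient and arm within patient, a within-arm covariance that lets nearby sites correlate more (AR(1) is one option), and site, side, sex, age and BMI as fixed effects. This also makes the patient the unit for age, BMI and sex.

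State whether both arms are scanned in every patient; if only one is, the arm term and the paired side comparison fall away. Define the groups to which between-groups ANOVA applies, and keep it for continuous outcomes measured once per patient, such as puncture time.

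The cost is a few lines of text and slightly more analysis work in the same software. No new data are needed.
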